6.3.1.2 Events of Clinical Interest

Selected non-serious and serious adverse events are also known as Events of Clinical Interest (ECI) and must be recorded as such on the Adverse Event case report forms/worksheets and reported within 24 hours to the Sponsor and within 2 working days to Merck Global Safety. (Attn: Worldwide Product Safety; [contact]) Events of clinical interest for this trial include:

1. An overdose of Merck product, as defined in Section 7.2.1 - Definition of an Overdose for This Protocol and Reporting of Overdose to the Sponsor, that is not associated with clinical symptoms or abnormal laboratory results.
2. an elevated AST or ALT lab value that is greater than or equal to 3X the upper limit of normal and an elevated total bilirubin lab value that is greater than or equal to 2X the upper limit of normal and, at the same time, an alkaline phosphatase lab value that is less than 2X the upper limit of normal, as determined by way of protocol-specified laboratory testing or unscheduled laboratory testing.*

*Note: These criteria are based upon available regulatory guidance documents. The purpose of the criteria is to specify a threshold of abnormal hepatic tests that may require an additional evaluation for an underlying etiology. The trial site guidance for assessment and follow up of these criteria can be found in the Investigator Trial File Binder (or equivalent).

1. Additional adverse events:

Product: Pembrolizumab and Lenalidomide
Protocol/Amendment No.: Version 3.1 July 18th, 2017

A separate guidance document has been provided entitled “Event of Clinical Interest Guidance Document” (previously entitled, “Event of Clinical Interest and Immune-Related Adverse Event Guidance Document”). This document can be found in Appendix 4 and provides guidance regarding identification, evaluation and management of ECIs and irAEs.

ECIs (both non-serious and serious adverse events) identified in this guidance document from the date of first dose through 90 days following cessation of treatment, or 30 days after the initiation of a new anticancer therapy, whichever is earlier, need to be reported within 24 hours to the Sponsor and within 2 working days to Merck Global Safety. (Attn: Worldwide Product Safety; [contact]), regardless of attribution to study treatment, consistent with standard SAE reporting guidelines.

Subjects should be assessed for possible ECIs prior to each dose. Lab results should be evaluated and subjects should be asked for signs and symptoms suggestive of an immune-related event. Subjects who develop an ECI thought to be immune-related should have additional testing to rule out other etiologic causes. If lab results or symptoms indicate a possible immune-related ECI, then additional testing should be performed to rule out other etiologic causes. If no other cause is found, then it is assumed to be immune-related.

6.3.2 Evaluating Adverse Events

An investigator who is a qualified physician will evaluate all adverse events according to the NCI Common Terminology for Adverse Events (CTCAE), version 4.0. Any adverse event which changes CTCAE grade over the course of a given episode will have each change of grade recorded on the adverse event case report forms/worksheets.

All adverse events regardless of CTCAE grade must also be evaluated for seriousness.

Table 7 Evaluating Adverse Events

An investigator who is a qualified physician, will evaluate all adverse events as to:

V4.0 CTCAE Grading	Grade 1	Mild; asymptomatic or mild symptoms; clinical or diagnostic observations only; intervention not indicated.
	Grade 2	Moderate; minimal, local or noninvasive intervention indicated; limiting age-appropriate instrumental ADL.
	Grade 3	Severe or medically significant but not immediately life-threatening; hospitalization or prolongation of hospitalization indicated; disabling; limiting self-care ADL.
	Grade 4	Life threatening consequences; urgent intervention indicated.
	Grade 5	Death related to AE
Seriousness	A serious adverse event is any adverse event occurring at any dose or during any use of Merck product that:	
	† Results in death ; or	
	† Is life threatening ; or places the subject, in the view of the investigator, at immediate risk of death from the event as it occurred (Note: This does not include an adverse event that, had it occurred in a more severe form, might have caused death.); or	
	† Results in a persistent or significant disability/incapacity (substantial disruption of one’s ability to conduct normal life functions); or	
	† Results in or prolongs an existing inpatient hospitalization (hospitalization is defined as an inpatient admission, regardless of length of stay, even if the hospitalization is a precautionary measure for continued observation. (Note: Hospitalization [including hospitalization for an elective procedure] for a preexisting condition which has not worsened does not constitute a serious adverse event.); or	
	† Is a congenital anomaly/birth defect (in offspring of subject taking the product regardless of time to diagnosis); or	
	Is a new cancer ; (that is not a condition of the study) or	
	Is an overdose (whether accidental or intentional). Any adverse event associated with an overdose is considered a serious adverse event. An overdose that is not associated with an adverse event is considered a non-serious event of clinical interest and must be reported within 24 hours.	
Other important medical events that may not result in death, not be life threatening, or not require hospitalization may be considered a serious adverse event when, based upon appropriate medical judgment, the event may jeopardize the subject and may require medical or surgical intervention to prevent one		

	of the outcomes listed previously (designated above by a †).	
Duration	Record the start and stop dates of the adverse event. If less than 1 day, indicate the appropriate length of time and units	
Action taken	Did the adverse event cause the Merck product to be discontinued?	
Relationship to test drug	
Did the Merck product cause the adverse event? The determination of the likelihood that the Merck product caused the adverse event will be provided by an investigator who is a qualified physician. The investigator's signed/dated initials on the source document or worksheet that supports the causality noted on the AE form, ensures that a medically qualified assessment of causality was done. This initialed document must be retained for the required regulatory time frame. The criteria below are intended as reference guidelines to assist the investigator in assessing the likelihood of a relationship between the test drug and the adverse event based upon the available information.
 
The following components are to be used to assess the relationship between the Merck product and the AE; the greater the correlation with the components and their respective elements (in number and/or intensity), the more likely the Merck product caused the adverse event (AE):
	
	Exposure	Is there evidence that the subject was actually exposed to the Merck product such as: reliable history, acceptable compliance assessment (pill count, diary, etc.), expected pharmacologic effect, or measurement of drug/metabolite in bodily specimen?
	Time Course	
Did the AE follow in a reasonable temporal sequence from administration of the Merck product?
 
Is the time of onset of the AE compatible with a drug-induced effect (applies to trials with investigational medicinal product)?

	Likely Cause	Is the AE not reasonably explained by another etiology such as underlying disease, other drug(s)/vaccine(s), or other host or environmental factors

Relationship to Merck product (continued)	The following components are to be used to assess the relationship between the test drug and the AE: (continued)	
	Dechallenge	
Was the Merck product discontinued or dose/exposure/frequency reduced?
 
If yes, did the AE resolve or improve?
 
If yes, this is a positive dechallenge. If no, this is a negative dechallenge.
 
(Note: This criterion is not applicable if: (1) the AE resulted in death or permanent disability; (2) the AE resolved/improved despite continuation of the Merck product; or (3) the trial is a single-dose drug trial); or (4) Merck product(s) is/are only used one time.)

	Rechallenge	
Was the subject re-exposed to the Merck product in this study?
 
If yes, did the AE recur or worsen?
 
If yes, this is a positive rechallenge. If no, this is a negative rechallenge.
 
(Note: This criterion is not applicable if: (1) the initial AE resulted in death or permanent disability, or (2) the trial is a single-dose drug trial); or (3) Merck product(s) is/are used only one time).
 
NOTE: IF A RECHALLENGE IS PLANNED FOR AN ADVERSE EVENT WHICH WAS SERIOUS AND WHICH MAY HAVE BEEN CAUSED BY THE MERCK PRODUCT, OR IF REEXPOSURE TO THE MERCK PRODUCT POSES ADDITIONAL POTENTIAL SIGNIFICANT RISK TO THE SUBJECT, THEN THE RECHALLENGE MUST BE APPROVED IN ADVANCE BY THE U.S. CLINICAL MONITOR AS PER DOSE MODIFICATION GUIDELINES IN THE PROTOCOL.

	Consistency with Trial Treatment Profile	
Is the clinical/pathological presentation of the AE consistent with previous knowledge regarding the Merck product or drug class pharmacology or toxicology?

The assessment of relationship will be reported on the case report forms /worksheets by an investigator who is a qualified physician according to his/her best clinical judgment, including consideration of the above elements.
		
Record one of the following	Use the following scale of criteria as guidance (not all criteria must be present to be indicative of a Merck product relationship).	
Yes, there is a reasonable possibility of Merck product relationship.	
There is evidence of exposure to the Merck product. The temporal sequence of the AE onset relative to the administration of the Merck product is reasonable. The AE is more likely explained by the Merck product than by another cause.
	
No, there is not a reasonable possibility Merck product relationship	
Subject did not receive the Merck product OR temporal sequence of the AE onset relative to administration of the Merck product is not reasonable OR there is another obvious cause of the AE. (Also entered for a subject with overdose without an associated AE.)
	

6.3.3 Sponsor Responsibility for Reporting Adverse Events

All Adverse Events will be reported to regulatory authorities, IRB/IECs and investigators in accordance with all applicable global laws and regulations.

7.0 STATISTICAL ANALYSIS PLAN

7.1 Phase I Statistical Analysis Plan

The primary objective of the Phase I portion of this trial is to identify the MTD (Phase II dose) which is the dose at which the estimated proportion of patients with DLTs is less than 0.33. The standard 3+3 design is employed. Patients will be treated in cohorts of 3 patients starting with Dose Cohort A with lenalidomide 15mg PO day 1-14 and pembrolizumab 200mg IV day 1, in cycles of 21 days, until disease progression or toxicity up to 24 months. The number of patients expected to be enrolled in the dose escalation study is 9 (up to 12 patients if unexpected toxicity is observed).

If 0 out of 3 patients at a particular dose level experiences a dose limiting toxicity (DLT) within Cycle 1 of treatment, if in Dose Cohort A (lenalidomide 15mg) dose escalation will proceed to cohort B (lenalidomide 20mg), if in Dose Cohort B, 3 additional patients will be added. If a DLT occurs in 0 of 6 patients enrolled on Dose Cohort B this will be deemed the Maximum Tolerated Dose (MTD).

If a DLT occurs in only 1 out of 6 patients enrolled at a particular dose level, dose escalation will occur, however, if this occurs on Dose Cohort B (lenalidomide 20 mg) or Dose Cohort Z (lenalidomide 10 mg), this will be deemed the Maximum Tolerated Dose (MTD). MTD is defined as the highest dose level at which < 33% of 6 patients experience a DLT.

If a DLT occurs in ≥ 2 of 3 patients or ≥ 2 of 6 patients treated on Dose Cohort A (lenalidomide 15mg), there will be a dose de-escalation to Dose Cohort Z (lenalidomide 10 mg).

If a DLT occurs in ≥ 2 of 3 patients or ≥ 2 of 6 patients treated on Dose Cohort B (lenalidomide 20 mg) or the preceding dose level will be declared the MTD if there were no more than 1 DLT in this previous cohort.

If a DLT occurs in ≥ 2 of 3 patients or ≥ 2 of 6 patients on Dose Cohort Z (lenalidomide 10mg), the trial will be discontinued and the expanded cohort will not be implemented.

Once the MTD has been determined, 17 additional patients with relapsed refractory HL will be treated in in the Phase II portion of this trial at the MTD.

While clinical benefit rates and other outcome rates for each dose cohort will be estimated, all of the summary of patient outcomes is descriptive.

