1.0 TRIAL SUMMARY

Abbreviated Title	Pembrolizumab and lenalidomide in Patients with Relapsed Refractory Non-Hodgkin and Hodgkin Lymphoma (HL)
Trial Phase	Phase I/II
Clinical Indication	Phase 1: Relapsed B cell HL and non-Hodgkin lymphoma (NHL); Phase 2: relapsed refractory (RR) HL
Trial Type	Therapeutic intervention
Type of control	n/a
Route of administration	Pembrolizumab IV; Lenalidomide PO
Trial Blinding	n/a
Treatment Groups	Phase 1: 9 patients expected (12 patients if unexpected toxicity) with relapsed HL and NHL Phase 2: 17 patients with RR HL
Number of trial subjects	26 (up to 29 if unexpected toxicity)
Estimated enrollment period	18-24 months
Estimated duration of trial	36-48 months
Duration of Participation	Until disease progression or toxicity up to 2 years

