2.0 TRIAL DESIGN

2.1 Trial Design

This is a Phase 1/2 open label study of the combination of pembrolizumab and lenalidomide and in patients with relapsed/refractory (RR) non-Hodgkin lymphoma (NHL) and Hodgkin lymphoma (HL).

Dose escalation will follow a standard 3+3 design. Patients will be treated in cohorts of 3 patients starting with Dose Cohort A with lenalidomide 15mg PO day 1-14 and pembrolizumab 200mg IV day 1, in cycles of 21 days, until disease progression or toxicity up to 24 months. The number of patients expected to be enrolled in the dose escalation study is 9 (up to 12 patients if unexpected toxicity is observed).

If 0 out of 3 patients at a particular dose level experiences a dose limiting toxicity (DLT) within Cycle 1 of treatment, if in Dose Cohort A (lenalidomide 15mg) dose escalation will proceed to cohort B (lenalidomide 20mg), if in Dose Cohort B, 3 additional patients will be added. If a DLT occurs in 0 of 6 patients enrolled on Dose Cohort B this will be deemed the Maximum Tolerated Dose (MTD).

If a DLT occurs in only 1 out of 6 patients enrolled at a particular dose level, dose escalation will occur, however, if this occurs on Dose Cohort B (lenalidomide 20 mg) or Dose Cohort Z (lenalidomide 10 mg), this will be deemed the Maximum Tolerated Dose (MTD). MTD is defined as the highest dose level at which < 33% of 6 patients experience a DLT.

[figure not shown]
If a DLT occurs in ≥ 2 of 3 patients or ≥ 2 of 6 patients treated on Dose Cohort A (lenalidomide 15mg), there will be a dose de-escalation to Dose Cohort Z (lenalidomide 10 mg).

[figure not shown]
If a DLT occurs in ≥ 2 of 3 patients or ≥ 2 of 6 patients treated on Dose Cohort B (lenalidomide 20 mg) or the preceding dose level will be declared the MTD if there were no more than 1 DLT in this previous cohort.

If a DLT occurs in ≥ 2 of 3 patients or ≥ 2 of 6 patients on Dose Cohort Z (lenalidomide 10mg), the trial will be discontinued and the expanded cohort will not be implemented.

Once the MTD has been determined, 15 additional patients with relapsed refractory HL will be treated in in the Phase II portion of this trial at the MTD.

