The combination of pembrolizumab and lenalidomide with low dose dexamethasone has been explored in multiple myeloma in the Keynote-023 study. In that study 33 patients who had failed ≥ 2 prior therapies were treated with the combination of pembrolizumab 200mg and lenalidomide at 10mg and 25mg. The therapy was well tolerated with no significant immune toxicity and no DLTs in 10mg lenalidomide cohort. In the 25-mg lenalidomide cohort, 3 patients (3/13) experienced a dose-limiting toxicity (DLT): neutropenia (grade 3 and grade 4), infectious pneumonia (grade 3), and tumor lysis syndrome (grade 3) with hyperuricemia (grade 4). All patients recovered from the DLTs without treatment discontinuation. Based upon these data the MTD/MAD was defined as pembrolizumab 200 mg fixed dose in combination with lenalidomide 25 mg and low-dose dexamethasone 40 mg. In this heavily pretreated patient population with a median follow-up of 287 days (48-476), 13/17 patients responded to treatment. The objective response rate (ORR) was 76%, with 4 patients achieving a very good partial response and 9 patients achieving a partial response. ORR has also been observed in patients with IMiDs-refractory and double refractory disease. (ASH abstract 505 Pembrolizumab in Combination with Lenalidomide and Low-Dose Dexamethasone for Relapsed/Refractory Multiple Myeloma (RRMM): Keynote-023).

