5.3.1.3 Definition of Dose-Limiting Toxicity

Toxicities should be attributable to the study intervention to constitute a dose limiting toxicity (DLT). Toxicity will be graded using the Common Toxicity Criteria for Adverse Events (CTCAE) version 4.0. A DLT is defined by the occurrence of any of the following toxicities (CTCAE v.4.03) for up to 21 days from initiation of the combination therapy (i.e. within the first cycle of therapy) in order to evaluate the potential toxicities of these therapies.

Non-Hematological dose-limiting toxicity

Any Grade 3 or Grade 4 non-hematological toxicity that is possibly, probably or definitely attributable to the regimen pembrolizumab-lenalidomide is considered a DLT, including the following:

- Any type of grade 3-4 hypersensitivity reaction (i.e.: allergic reaction, anaphylaxis, serum sickness, skin disorders, etc.), regardless of attribution.
- Any type of grade 3-4 immune related adverse event
- Inability to receive pembrolizumab-lenalidomide therapy within a 1 month period of scheduled treatment, due to a therapy related event.
- Grade 3 nausea/vomiting/diarrhea lasting longer than 24hours despite maximal care or Grade 4 nausea/vomiting/diarrhea

Any other non-hematologic clinical toxicity considered at least possibly related to treatment defined as any Grade 3 or greater with the specific exception of:

- Grade 3 dehydration that, in the opinion of the investigator, occurs in the setting of inadequate prophylactic measures or compliance with supportive care measures and lasts for less than 48 hours
- Grade 3 fatigue or Grade 4 fatigue that lasts for ≤ 5 days
- Grade 3 fever
- Grade 3 ALT/AST elevation for which total bilirubin remains within normal limits.

Hematologic dose-limiting toxicity

The following hematological toxicity possibly, probably or definitely attributable to the regimen of pembrolizumab and lenalidomide is considered a DLT. Growth factors are allowed per treating investigator's discretion in patients at high risk for febrile neutropenia.

- Grade 4 neutropenia associated with fever (> 38.5) of any duration
- Grade 3 neutropenia associated with fever (> 38.5) of any duration
- Grade 4 thrombocytopenia or Grade 3 thrombocytopenia with bleeding or any requirement for platelet transfusion.
- Grade 4 anemia unexplained by underlying disease
- Myelosuppression that causes a delay of > 7 days in next cycle of pembrolizumab/lenalidomide

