The principal investigator will conduct bi-weekly meetings with the research team, to monitor toxicity while there are active patients. The study will be reviewed by the NYU Perlmutter Cancer Center Data and Safety Monitoring Committee (DSMC). The DSMC reviews all data for patient safety according to the DSMC policies. This review includes an examination of patient accrual, adverse events and study results. For phase I, dose finding trials, a review of toxicity after the first defined cohort is conducted to assure no DLTs are found before proceeding to the next cohort, per the protocol definition. If additional cohorts are required to establish the recommended dose for the extended safety cohort or phase II component of a phase I/II trial, these cohorts will be evaluated in a similar manner. By definition, dose finding cohort data will have to be confirmed or extended, by the trial definition, prior to proceeding to the next treatment group. Reviews will be done within 2-3 days of the complete cohort data set being available, even if not coinciding with a scheduled monthly meeting, so as to not delay study accrual. Once the recommended dose is established, further interim reviews will be performed at accrual points established by the protocol. All studies are required to be reviewed at least annually, regardless of their accrual status. Principal Investigators are required to attend the review of their studies.

All sites will participate in a bi-weekly teleconference to discuss all toxicities for all patients enrolled up to cycle 5 of therapy.

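### The MTD is defined on 6 patients, but the written fall-back can declare Cohort A the MTD on 3; a minor companion gap is that the cycle 2 delay criterion resolves after the 21-day DLT window

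*Combined protocol and SAP*

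**What the plan says.** Sections 2.1 and 7.1 carry the same escalation rules. Both state: "MTD is defined as the highest dose level at which < 33% of 6 patients experience a DLT". With 6 patients, that means at most 1 DLT. Section 7.1 also opens with a looser target, an estimated DLT proportion below 0.33, with no number of patients attached.

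After 0 of 3, the two cohorts are treated differently. Cohort A (lenalidomide 15 mg) goes straight to Cohort B (20 mg). For Cohort B the rule is "if in Dose Cohort B, 3 additional patients will be added". If Cohort B has at least 2 DLTs in 3 or in 6, "the preceding dose level will be declared the MTD if there were no more than 1 DLT in this previous cohort". That sentence is garbled in both sections just before the quoted words, and it sets no minimum size for the previous cohort.

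Section 1.0 gives the size as "Phase 1: 9 patients expected (12 patients if unexpected toxicity) with relapsed HL and NHL". Section 8.1 adds that "dose finding cohort data will have to be confirmed or extended, by the trial definition, prior to proceeding to the next treatment group".

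On timing, section 5.3.1.3 counts DLTs "for up to 21 days from initiation of the combination therapy (i.e. within the first cycle of therapy"). Its list nevertheless includes myelosuppression that delays the next cycle by more than 7 days, and inability to be treated within a month of schedule.

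**The concern.** Finding the MTD is the Phase 1 primary objective, and the result sets the dose for the 17 Phase 2 patients. On one path (Cohort A 0/3, Cohort B at least 2 DLTs) the declaration rule is satisfied while the 6-patient definition is not. Two teams following the text could act differently: one would open Phase 2 at 15 mg, the other would look for a step that enrols 3 more patients and find none.

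The timing gap is smaller. A patient with Grade 4 neutropenia without fever has lenalidomide held under Table 4, but has a DLT only through a delay criterion. That criterion cannot yet be judged when the 21-day window closes, and the text does not say that escalation must wait.

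**Working it through.** **Stated sizes.** The written rule reproduces the plan's figures. With no DLTs, 3 (A) + 6 (B) = 9. The largest paths are A 6 + B 6 = 12 and A 6 + Z 6 = 12. Cohort A can be declared on 3 patients with 6 patients in total (B stops at 3) or 9 (B reaches 6).

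**Inputs.** The rules come from 7.1. The true DLT rates pA and pB are assumptions; the documents give none for this combination in lymphoma. The only combination data cited (section 4.1.3, myeloma, with dexamethasone) are "no DLTs in 10mg lenalidomide cohort" and 3 of 13 at 25 mg, so 3/13 is used as one value for pB. As in a standard 3+3, 1 DLT in the first 3 is assumed to add 3 patients; the text implies this without stating it.

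**Formulas.**
- P(A declared on 3) = (1 − pA)³ × P(X ≥ 2 | 6, pB).
- Decision changed by filling A = that × P(X ≥ 2 | 3, pA), because after 0/3 only 2 or 3 DLTs in the next 3 give at least 2 of 6.
- Share of A declarations after B fails that rest on 3 = 1 / [1 + 3pA(1 − pA)²].

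| pA, pB | A declared on 3 | Decision changed | Share on 3 |
|---|---|---|---|
| 0.05, 0.10 | 0.857 × 0.114 = 0.098 | × 0.007 = 0.0007 | 0.88 |
| 0.10, 0.20 | 0.729 × 0.345 = 0.251 | × 0.028 = 0.0070 | 0.80 |
| 0.10, 3/13 | 0.729 × 0.420 = 0.306 | × 0.028 = 0.0086 | 0.80 |
| 0.15, 3/13 | 0.614 × 0.420 = 0.258 | × 0.061 = 0.0157 | 0.75 |
| 0.20, 0.40 | 0.512 × 0.767 = 0.393 | × 0.104 = 0.041 | 0.72 |
| 0.33, 0.50 | 0.301 × 0.891 = 0.268 | × 0.255 = 0.068 | 0.69 |
| 0.40, 0.50 | 0.216 × 0.891 = 0.192 | × 0.352 = 0.068 | 0.70 |

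These ranges are not bounds. A steeper pair, (0.10, 0.33), gives 0.468 declared on 3 and 0.468 × 0.028 = 0.013 changed.

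**Precision.** The exact two-sided 95% upper limit is 1 − 0.025^(1/3) = 0.708 for 0/3 and 1 − 0.025^(1/6) = 0.459 for 0/6. Neither excludes 33%.

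**Direction of the change.** On this path, filling A can only turn a declaration into a rejection. That is right if the true rate at A exceeds 0.33 and wrong if it is lower. Only one of the seven pairs has pA above 0.33.

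**Timing.** With 21-day cycles, cycle 2 is due on day 22. A delay of more than 7 days is first established on day 22 + 8 = 30, which is 9 days after the window closes. The 1-month criterion falls at about day 31 if counted from day 1, or day 52 if counted from day 22.

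**The case against.** The strongest reply is that the fill step may exist where we cannot see it. Two figures within the section 2.1 rules and the diagram in 2.2 are not shown, the Cohort B sentence is damaged, and the cap of 12 would fit A 3 + B 6 + A 3. This stands as a limit: the finding concerns the written text. It does not remove the need for a sentence in 7.1. The 8.1 requirement to confirm or extend cohort data refers back to the trial's own rule and adds no step.

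A reader might infer that the plan plainly breaches its own definition. The documents do not support that without qualification, because the opening sentence of 7.1 has no denominator and 0/3 satisfies it. The two statements are unreconciled.

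A reader might also infer that a 3-patient MTD is unsafe, or passes on a laxer standard. At a true rate of 0.33, P(0/3) = 0.30 and P(≤ 1/6) = 0.36, so 0/3 is not the easier mark there. In six of the seven pairs pA is at or below 0.33, so most changed decisions would discard a dose at or under the threshold.

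On timing, a reader might infer that delay-based DLTs will be missed. The ordinary reading takes the cycle 1 toxicity as the event and the delay as its qualifier, and the complete cohort data that 8.1 calls for can include a pending delay. A permanent stop in cycle 1 could settle the 1-month criterion early. Day 8 and day 15 blood counts, pre-dose laboratory review, bi-weekly toxicity meetings and cohort-by-cohort DSMC review also limit the consequence. What remains is that no sentence holds escalation until the delay is known.

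**Conclusion.** The point holds as an inconsistency in the written dose-finding rule. When Cohort A is 0/3 and Cohort B then fails, the fall-back declares A on 3 patients although the stated definition uses 6. Under the seven assumed pairs this occurs in about 0.10 to 0.39 of trials. At pA from 0.10 to 0.40, about 69% to 80% of A declarations after B fails rest on 3 patients (88% at pA 0.05).

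The effect on decisions is small, about 0.1% to 7% of trials, and about 0.7% to 1.6% for the pairs nearest the cited myeloma data (pA 0.10 to 0.15, pB 0.20 to 3/13). The case for changing the text is consistency and a tighter estimate of the DLT rate at the chosen dose. All these probabilities depend on assumed rates and on expansion after 1 of 3.

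The timing point is real but minor, and any undercount of DLTs cannot be quantified from the documents. Both are worth correcting; neither calls the design into question.

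**What to change.** In 2.1 and 7.1, repair the Cohort B sentence and add: *if Cohort A has only 3 patients, treat 3 more and declare it the MTD only if no more than 1 of 6 has a DLT.* Reconcile the opening sentence of 7.1 with the 6-patient definition.

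Restate the maximum sample size. If the enlarged Cohort A passes, the total is A 6 + B 6 = 12 at most, within the present cap. If it fails and Cohort Z opens, Phase 1 can reach 6 + 6 + 6 = 18 and the trial 18 + 17 = 35, against the stated 12 and 29. That branch opens in about 0.1% to 7% of trials under the assumed rates.

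Averaged over trials, the extra enrolment is at most 3 × P(A on 3) + 6 × P(changed). This runs from 3 × 0.098 + 6 × 0.0007 = 0.3 patients at (0.05, 0.10) to 3 × 0.393 + 6 × 0.041 = 1.4 at (0.20, 0.40). The affected path also waits for 3 more patients to be accrued and complete a 21-day DLT window.

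In 5.3.1.3, as a minor change, state that a cycle 2 delay caused by a toxicity arising in cycle 1 counts as a cycle 1 DLT, and say from which date the 1-month criterion runs. Make no cohort decision until each patient has started cycle 2 or the more-than-7-day criterion is resolved. The cost is wording, plus a wait of up to about 8 days (day 22 to day 30) when a patient's cycle 2 is held.
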